#### 4.3.2.1 Dose escalation criteria and Dose Limiting Events

Dose escalation will be managed according to review of available and emerging data on the subjects administered ATIMP top date and the occurrence, if any, of DLE's or medically important events. An SDMC will review data from a minimum of 6 weeks of follow up from each cohort of participants (at least one older child, 11-15 years of age per cohort), before recommending the next dose to be assessed in a further cohort of participants or to additional participants at the same dose level.

A DLE is defined as any of the below occurring during the 6 weeks following administration, at least possibly related to the ATIMP, not surgery alone:

- A reduction in visual acuity by 15 ETDRS letters or more that fails to resolve to within 15 letters of baseline in a 4-week period once prophylactic treatment commences
- Severe unresponsive inflammation (defined below)\*
- Infective endophthalmitis
- Ocular malignancy
- Grade III or above non-ocular SUSAR (see section 5.11.3)

\* Severe unresponsive inflammation will be defined according to the Standardisation of Uveitis Nomenclature (SUN) Working Group grading system (Jabs *et Al.* 2005) i.e.

- anterior chamber cells 3+ (26-50 cells in a field size of 1mm x 1-mm slit-beam), or
- anterior chamber flare 3+ (marked, iris and lens details hazy), or
- vitreous haze 3+ (Ophthalmology 1985; 92:467-71)

that fails to improve by 2 steps (or to grade 0) during a 6-week period.

Review of safety data will be undertaken by the SDMC prior to each dose escalation.

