#### 4.3.2.2 Dosing process

##### 4.3.2.2.1 Cohort 1

ATIMP will first be administered at the lowest dose to at least one older paediatric (aged 11-15) participant only. This participant will be monitored for signs or evidence of visual and/or systemic toxicity for a period of 6 weeks and as per schedule of assessments (section 5.6). If there is no DLE as

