## Gene Therapy for Achromatopsia (CNGA3)

---

defined above after a minimum of 6 weeks, ATIMP will continue to be administered at the same dose to 2 additional paediatric participants. In the event of a DLE in the first cohort, a discussion will be held with the SDMC to agree a plan of action for the administration of ATIMP to further participants. The SDMC will review the data collected on this cohort up to 6 weeks following ATIMP administration to the last participant in the cohort.

### 4.3.2.2.2 Cohort 2

In the event that there is no DLE or other event considered clinically relevant to the progression of the study and dose escalation in any participant in cohort 1 the SDMC will provide a recommend to proceed administering ATIMP at the intermediate dose level. If dose escalation proceeds, at least a single older paediatric (aged 11-15) participant will be administered ATIMP. If there is no DLE or other event considered clinically relevant after a minimum of 6 weeks, ATIMP will continue to be administered at the same dose to 2 further participants. In the event of a DLE in the first participant in the cohort, a discussion will be held with the SDMC to agree a plan of action for administering the ATIMP to further participants. The SDMC will again review the data available on this next cohort of participants up to 6 weeks following ATIMP administration to the last participant in the cohort.

### 4.3.2.2.3 Cohort 3

In the event that there is no DLE (or clinically relevant event) in any participant in previous cohorts, the SDMC may recommend administering ATIMP at the highest dose level to a single older paediatric participant (aged 11-15 years) following review of all presented safety, toxicity and if relevant efficacy data. If there is no DLE or other event considered clinically relevant to the progression of the study after a minimum of 6 weeks, ATIMP will be administered at the same dose to 2 further participants. In the event of a DLE in the first participant in the cohort, a discussion will be held with the SDMC to agree a plan of action for administering the ATIMP to further participants, the age and the dose.

[figure not shown]

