### 4.3.2.2.5 Additional considerations

In the event of a DLE in one of the participants at a given dose, the cohort may be expanded at the same dose level. The SDMC will review the safety data and recommend that additional participants may be treated at this dose. The SDMC may recommend that the same dose of ATIMP is administered to additional participants. The dose escalation will continue until SDMC are comfortable on review of the accumulating data, to recommend a maximum dose to be administered, or 3 participants have been administered the highest dose without any DLEs, or until at least 2 participants among a cohort of 3 to 6 participants experience DLEs (i.e.,  $\geq 33\%$  of patients with a DLE at that dose level), in which case the recommended dose will be the level below this dose. In the event that 1 or 2 DLEs are seen at the first dose level, the SDMC may recommend administering a lower dose to that described in the protocol to a cohort of participants.

Table 1: Dose escalation table

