## 5.5 Outcomes

### 5.5.1 Primary Outcomes

The primary outcome is defined as any of the below occurring during the 6 weeks following administration, at least possibly related to the ATIMP, not surgery alone:

- Reduction in visual acuity by 15 ETDRS letters or more that fails to resolve to within 15 letters of baseline in a 4-week period once prophylactic treatment commences
- Severe unresponsive inflammation
- Infective endophthalmitis
- Ocular malignancy
- Grade III or above non-ocular SUSAR (see section 5.11.3)

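### If the inflammation response clock starts at the first 3+ grade, a case unimproved at day 42 is not yet a DLE, and Cohort 1's first-participant gate tests only for DLEs

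*Protocol*

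**What the plan says.** Protocol 4.2.1 and 4.3.2.1 define severe unresponsive inflammation as anterior chamber cells, flare or vitreous haze at SUN grade 3+ "that fails to improve by 2 steps (or to grade 0) during a 6-week period". Neither section says when the 6 weeks begin. The visual acuity item in the same list does name a starting event: "in a 4-week period once prophylactic treatment commences". SAP 2.1 refers back to the protocol definition and adds nothing on timing.

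All DLE components share one window. Protocol 5.5.1 reads: "The primary outcome is defined as any of the below occurring during the 6 weeks following administration". Neither document says whether a component that needs a response period is placed in that window by its onset or by the date non-response is confirmed.

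The gates use the same length of time. In 4.3.2.2.1, for the first child in Cohort 1: "This participant will be monitored for signs or evidence of visual and/or systemic toxicity for a period of 6 weeks". If there is no DLE "defined above after a minimum of 6 weeks, ATIMP will continue to be administered at the same dose to 2 additional paediatric participants". The way out of Cohort 1 is wider and requires "no DLE or other event considered clinically relevant to the progression of the study and dose escalation in any participant in cohort 1" (4.3.2.2.2). The first-participant gates in Cohorts 2 and 3 likewise let a clinically relevant event other than a DLE hold up dosing. Section 4.3.2.2.5 then uses formal DLE status in two counts that end escalation. One is met when "3 participants have been administered the highest dose without any DLEs". The other, which sets the recommended dose one level lower, lets escalation run "until at least 2 participants among a cohort of 3 to 6 participants experience DLEs".

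**The concern.** Non-response that takes 6 weeks to establish cannot always be established inside a 6-week window that opened earlier. If the response clock starts when 3+ inflammation is first graded, a child whose inflammation has not improved by day 42 is, by definition, neither a DLE nor clear of one. The visible text has no category for that child, so a literal reader records no DLE.

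Most gates tolerate this because they also look at other relevant events. The Cohort 1 first-participant gate does not. Its visible wording tests only for a DLE, and a DLE is the only stated trigger for an SDMC discussion at that step. This is also the first use of this vector in a patient (Protocol 4.1.3). At stake is dosing two more children at the lowest dose while the only treated child has unresolved 3+ inflammation.

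Late onset is plausible on the protocol's own schedule. Oral steroid is tapered through week 4 (5.4.1.5), and routine topical and systemic immunosuppression then stops (5.4.2.3). Inflammation that emerges after the taper would first be graded at about W4 or W6, where the pending time is longest.

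**Working it through.** **Inputs.** The response period, the DLE window and the minimum gate are each 6 weeks = 42 days (4.3.2.1, 4.3.2.2.1). Table 2 puts administration on Day 0, with ocular examinations at D1, D3, W1, W2, W4, W6, W12 and W24. The visit windows are ±7 days at W6 and ±14 days at W12 and W24. No ocular examination is scheduled between W6 and W12.

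**Day numbering.** SAP 3.3 calls the day of administration Day 1, so the SAP target day is 7 × weeks + 1. For week 6 this is 7 × 6 + 1 = 43, as SAP Table 1 states, which is protocol day 42. The targets for weeks 1, 2, 4, 12 and 24 (8, 15, 29, 85, 169) also reproduce. Protocol days are used below.

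**Two possible clock starts, for a case that does not improve.**

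| First 3+ grade | Day | Clock from that grade: confirmed on day + 42 | Days past day 42 | Clock from surgery: response time at day 42 = 42 − day |
|---|---|---|---|---|
| D1 | 1 | 43 | 1 | 41 |
| D3 | 3 | 45 | 3 | 39 |
| W1 | 7 | 49 | 7 | 35 |
| W2 | 14 | 56 | 14 | 28 |
| W4 | 28 | 70 | 28 | 14 |
| W6 | 42 | 84 | 42 | 0 |

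With the clock at first grade, none of the six is confirmed by day 42. With the clock at surgery, all are classifiable on day 42, but late onsets have had little or no time to respond. A case that has already improved by 2 steps or to grade 0 is settled as not a DLE on either reading.

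**What later visits settle (clock at first grade).** Latest onset settled = visit day − 42.
- W6 on day 35, 42 or 49: none, none, day 7.
- W12 on day 70, 84 or 98: day 28, 42, 56.
- W24 at its earliest, 168 − 14 = day 154: day 112, which covers every onset in the 42-day window.

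**Effect at each decision.**
- *Cohort 1, first participant.* At the 42-day minimum, any unimproved case first graded on D1 or later is pending. Two children at the same dose follow.
- *End of a cohort.* The first participant then has at least 42 + 42 = 84 days of follow-up, enough for any onset up to day 42. Only the later two can be pending.
- *Next cohort.* One older child is dosed at the review, when the last earlier participant is at 42 days. The next two follow at least 42 days later, when that participant is at 84 days and 84 − 42 = 42, so every onset in the window is settled. Typically one child is exposed before status is known.
- *Highest dose.* The third participant can be pending for up to 84 − 42 = 42 days after the earliest review.

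**The case against.** The strongest reply is that the gap depends on one reading of the clock. The DLE list is framed by the 6 weeks after administration, and 5.4.2.3 describes the expected course of inflammation relative to surgery, so the same 6 weeks may be meant for both. Every case could then be classified on day 42, and late onsets would count as DLEs, which errs toward caution. That reading is possible. The text does not choose it, and it would label a W6 onset unresponsive after 0 days.

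Next, the gates are minimums, and persistent 3+ inflammation in the only treated child would be obvious. The monitoring in 4.3.2.2.1 covers toxicity more broadly than DLEs. Section 4.3.2.1 has escalation weigh medically important events. Section 5.4.2.3 requires prolonged or severe inflammation to be investigated and treated, 5.11.3.2 promises prompt review of safety events, and 5.4.9.2 lets the Chief Investigator or sponsor stop the trial. All of this stands and makes harm unlikely. It supplies treatment and discretion, but does not change what the first-participant gate requires.

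Third, the highest-dose count has little safety effect. No higher dose can follow, a single late DLE among three does not reach the 2-DLE rule, and follow-up to W24 would correct the record. This also stands.

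Finally, the SDMC Charter is a separate document (5.11.1), and the dose-escalation table does not appear in the available text. Either may deal with pending cases, so the statement that this gate names only a DLE is limited to the visible text.

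**Conclusion.** The point holds, at minor to moderate severity. Assuming the clock starts at the first 3+ grade, a case still unimproved on day 42 is confirmed on day 43 at the earliest and day 84 at the latest. Its formal status is therefore open at a gate held at the minimum time. The consequence that matters is at the Cohort 1 first-participant gate: read literally, two more children at the lowest dose. Escalation between cohorts is largely covered by the wider clauses and the stagger. The count at the highest dose could be provisional for up to 42 days.

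Three stronger inferences are not supported.
- *No case can be classified at day 42.* Improved cases are already settled, and a W6 visit or gate on day 49 settles unimproved onsets up to day 7.
- *The inflammation component can never count toward the primary outcome.* That would require dating the event at confirmed non-response. SAP 3.6 ties an event's occurrence to its onset, so onset dating is the more natural reading. On that reading W12 and W24 supply the missing information, and the final analysis is not materially affected.
- *The escalation scheme as a whole ignores pending inflammation.* The Cohort 2 and 3 wording and the SDMC's wider remit say otherwise.

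**What to change.** 1. In 4.3.2.2.1, let a clinically relevant event other than a DLE also hold up dosing after the first participant, as the Cohort 2 and 3 gates already do.
2. In 4.3.2.1, define the component as a first 3+ grade within 6 weeks of administration, with the 6-week response period starting at that grade and the event dated to onset. Carry this to 4.2.1, 5.5.1, 5.10.3.2 and SAP 2.1. Response can be judged at W12, W24 or an unscheduled visit; SAP 3.4 already allows extra visits to be used for clinically important outcomes.
3. At every gate, and in the 4.3.2.2.5 counts, do not record a participant with unimproved 3+ inflammation still inside the response period as free of a DLE until the case resolves or the SDMC has reviewed it.

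The cost is wording and, only when such a case is pending, a dosing delay of up to about 6 weeks and occasionally one unscheduled visit (for example, W12 held on day 70 with onset after day 28). The final analysis is not delayed. SAP 1.2 describes dosing partly in the past tense. If dosing is complete, the gate changes no longer matter for this trial, but the definition and the onset-dating rule still do.

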#### 4.3.2.2 Dosing process

##### 4.3.2.2.1 Cohort 1

ATIMP will first be administered at the lowest dose to at least one older paediatric (aged 11-15) participant only. This participant will be monitored for signs or evidence of visual and/or systemic toxicity for a period of 6 weeks and as per schedule of assessments (section 5.6). If there is no DLE as

## Gene Therapy for Achromatopsia (CNGA3)

---

defined above after a minimum of 6 weeks, ATIMP will continue to be administered at the same dose to 2 additional paediatric participants. In the event of a DLE in the first cohort, a discussion will be held with the SDMC to agree a plan of action for the administration of ATIMP to further participants. The SDMC will review the data collected on this cohort up to 6 weeks following ATIMP administration to the last participant in the cohort.

### 4.3.2.2.2 Cohort 2

In the event that there is no DLE or other event considered clinically relevant to the progression of the study and dose escalation in any participant in cohort 1 the SDMC will provide a recommend to proceed administering ATIMP at the intermediate dose level. If dose escalation proceeds, at least a single older paediatric (aged 11-15) participant will be administered ATIMP. If there is no DLE or other event considered clinically relevant after a minimum of 6 weeks, ATIMP will continue to be administered at the same dose to 2 further participants. In the event of a DLE in the first participant in the cohort, a discussion will be held with the SDMC to agree a plan of action for administering the ATIMP to further participants. The SDMC will again review the data available on this next cohort of participants up to 6 weeks following ATIMP administration to the last participant in the cohort.

### 4.3.2.2.3 Cohort 3

In the event that there is no DLE (or clinically relevant event) in any participant in previous cohorts, the SDMC may recommend administering ATIMP at the highest dose level to a single older paediatric participant (aged 11-15 years) following review of all presented safety, toxicity and if relevant efficacy data. If there is no DLE or other event considered clinically relevant to the progression of the study after a minimum of 6 weeks, ATIMP will be administered at the same dose to 2 further participants. In the event of a DLE in the first participant in the cohort, a discussion will be held with the SDMC to agree a plan of action for administering the ATIMP to further participants, the age and the dose.

[figure not shown]

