### 4.3.2.2.2.4 Adult Cohort-United States

In addition to the paediatric cohorts in the United Kingdom an additional cohort of 2 adult subjects, 18 years of age or older will be administered ATIMP at the highest dose studied from the paediatric cohorts based on when the first adult subject is identified and ready to be enrolled. The SDMC will also review the data from the adult cohort.

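### After a dose-limiting event the readable protocol calls for SDMC review but states no dosing hold; cohorts 2 and 3 name only the first participant as trigger, and adult dosing carries no DLE condition

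*Protocol*

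**What the plan says.** Protocol section 4.3.2.2 sets the dosing order within each cohort.

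- **Cohort 1 (4.3.2.2.1).** One older child is dosed and observed for 6 weeks. If there is no DLE, "ATIMP will continue to be administered at the same dose to 2 additional paediatric participants". The trigger covers the whole cohort: "In the event of a DLE in the first cohort, a discussion will be held with the SDMC".
- **Cohorts 2 and 3 (4.3.2.2.2 and 4.3.2.2.3).** The sequence is the same. In cohort 2, after a clear 6 weeks, "ATIMP will continue to be administered at the same dose to 2 further participants"; cohort 3 is worded almost identically. The trigger in both is narrower: "In the event of a DLE in the first participant in the cohort, a discussion will be held with the SDMC". No interval is stated between the second and third participants.
- **Adult cohort in the US.** Two adults "will be administered ATIMP at the highest dose studied from the paediatric cohorts based on when the first adult subject is identified" and ready. The SDMC also reviews the adult data. The section states no DLE condition for dosing.
- **General rule (4.3.2.2.5).** "In the event of a DLE in one of the participants at a given dose, the cohort may be expanded" at that level, and "The SDMC will review the safety data and recommend that additional participants may be treated at this dose". Escalation continues "until at least 2 participants among a cohort of 3 to 6 participants experience DLEs", among other end conditions; in that case the recommended dose is the level below.
- **Review before the next step (4.3.2.1).** The SDMC sees at least 6 weeks of data from each cohort before it recommends the next dose, or additional participants at the same dose.

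**The concern.** The trigger narrows at the two higher doses. Section 4.3 has at least one child aged 11 to 15 dosed first in each cohort before younger children. The second and third participants may therefore be the first younger children at that dose, yet in cohorts 2 and 3 the cohort paragraph names only a DLE in the first participant. If participant 2 has a DLE, the reader has to find the rule in another section, and that rule does not say whether participant 3 waits.

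The adult section raises the same question more sharply, because it refers to the highest dose studied, not the highest dose cleared.

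Administration is a single surgical dose that cannot be withdrawn. What is at stake is the order of events: the SDMC's decision should come before the next dose. The decision may still be to dose, since the design tolerates one DLE at a level.

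**Working it through.** The protocol gives no figure on this point, so the check is mainly textual, with an illustration of size.

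**Step 1: is a DLE in participant 2 of cohort 2 or 3 reviewed?** Yes. Section 4.3.2.2.5 applies to any one participant at a dose. Section 4.3.2.1 puts SDMC review before additional participants at the same dose. The cohort 1 paragraph uses the word 'additional' for planned participants 2 and 3, so the more natural reading of both sections includes planned participant 3. Cohort 2 also has a review at the end of the cohort; the cohort 3 paragraph lacks that sentence.

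**Step 2: is dosing held until that review?** No readable section says so.

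- 4.3.2.2.5 gives the review no timing.
- 4.3.2.1 is a rule about cohort data, not a pause after an event.
- The rule of at least 2 DLEs ends escalation and does not act on a single DLE.
- 4.1.5 mentions an appropriate interval between successive participants but gives no length.
- 5.11.3.2 promises prompt review of safety events, not a pause.
- Urgent safety measures (5.11.3.6.2) and termination (5.4.9.2) are discretionary.
- The cohort 1 paragraph itself requires a discussion, not a hold.

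**Step 3: the adult cohort.** Suppose 2 of 3 children at the high dose have DLEs. The rule in 4.3.2.2.5 (2/6 = 33.3%, which matches the percentage printed there; here 2/3 = 66.7%) makes the intermediate dose the recommended one. The highest dose studied is still the high dose. Read literally, an adult who is then ready would receive a dose above the recommended level. With a single DLE still awaiting review, the adult section alone does not defer dosing either.

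**Step 4: how often the paediatric situation arises.** Let p be the DLE probability per participant. The documents give none, so p is an assumption. Assume equal and independent risk, dosing one at a time, and a DLE in participant 2 that is established before participant 3 is dosed.

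- Participant 1 clean, participant 2 with a DLE: p(1 − p).
- The same, and participant 3 also with a DLE: p²(1 − p).

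| p | p(1 − p) | p²(1 − p) |
|---|---|---|
| 0.05 | 0.05 × 0.95 = 4.75% | 0.0025 × 0.95 = 0.24% |
| 0.10 | 0.10 × 0.90 = 9.0% | 0.01 × 0.90 = 0.9% |
| 0.20 | 0.20 × 0.80 = 16.0% | 0.04 × 0.80 = 3.2% |
| 1/3 | 1/3 × 2/3 = 22.2% | 1/9 × 2/3 = 7.4% |

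These are upper bounds for a given p. The first column counts how often the question would come up, not harm. The second bounds what a hold could avert, because the SDMC may release participant 3 after review. Two of the five DLE criteria are established only after a period without resolution (4 weeks for visual acuity, 6 weeks for inflammation). The other three (infective endophthalmitis, ocular malignancy, and a non-ocular SUSAR of Grade III or above) carry no such wait.

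**The case against.** The strongest case is that the protocol, read as a whole, already puts the SDMC between a DLE and the next dose. Sections 4.3.2.1 and 4.3.2.2.5 both speak of additional participants, a term that the protocol itself uses for planned participants. The release condition in cohorts 2 and 3 is the absence of a DLE or other clinically relevant event, and its words are not expressly confined to participant 1. Entry to cohorts 2 and 3 is already conditional on no DLE in any participant of the preceding cohorts. Serious events are notified within 24 hours, and the medical monitor and principal investigator support the SDMC. The first listed circumstance for termination could cover a serious ATIMP-related DLE, since no event is considered expected for the product. Section 4.3.2.2.5 works by dose, not age, so it can be read to reach adults. Finally, the figure after the cohort 3 paragraph, the body of Table 1 and the SDMC charter are where a hold would most likely be stated.

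Much of this stands. A reader might infer from the cohort 2 and 3 paragraphs that a DLE in a later participant goes without SDMC review; sections 4.3.2.1 and 4.3.2.2.5 contradict that. A reader might also infer that the trial has no hold at all; the missing material means that this cannot be said. The objection does not supply a sentence saying that dosing waits, and it does not remove the difference in triggers. Nor does it add a DLE condition to the adult section: the SDMC's review of adult data is stated, but not that review must come before adult dosing after a paediatric DLE.

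**Conclusion.** The point holds as an inconsistency and a missing hold in the readable text, not as missing review. The cohort 2 and 3 triggers are narrower than the cohort 1 trigger. The general rules probably cover planned participant 3 but do not say that dosing pauses. The adult section is the weakest place, because its literal wording permits dosing at a level with an unreviewed DLE, or above the recommended dose.

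The benefit of a change is small and confined to DLEs established before the next participant is dosed. It is bounded by 4.75% to 22.2% of cohorts for the situation, and by 0.24% to 7.4% for a further DLE in participant 3. Both ranges rest on assumed, equal and independent DLE rates of 5% to 1/3. They describe a paediatric cohort of three and do not size the adult question. Confidence is medium, because the charter, Table 1 or the figure may already settle the matter. The change is still worth making: the trial is the first in humans with this product, its participants are mostly children, and the dose cannot be withdrawn.

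**What to change.** 1. In the cohort 2 and cohort 3 paragraphs, change the trigger from *the first participant in the cohort* to *any participant in the cohort*.
2. Add to section 4.3.2.2.5: *After any DLE, no further participant (planned, expansion or adult cohort) is dosed at that dose level or higher until the SDMC has reviewed it.*
3. Check the SDMC charter and Table 1, and align them if they differ.

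The second change does the real work; the first alone would add only a discussion. The cost is a few words in two paragraphs, one sentence, a check of the charter, and a possible short dosing pause after a DLE. The change does not reach a DLE that is established only after the next participant has been dosed. If the charter already contains a hold, the edit simply brings the protocol into line with it.
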